9.3 Response Criteria for Primary and Secondary Endpoints

9.3.1 PSA

For each patient, use a waterfall plot to report the percent change in PSA from baseline to 12 weeks (or earlier for those who discontinue therapy) and the maximum decline in PSA that occurs at any point after treatment. We will also report the proportion of patients to achieve a 50% or greater decrease in PSA from baseline (i.e. PSA₅₀ response rate).

9.4 Criteria for Progressive Disease.

9.4.1 Radiographic Progression

Radiographic progression is defined at the development of metastatic disease observed on CT and/or Bone Scan.

10. DATA REPORTING AND REGULATORY REQUIREMENTS

Multicenter Guidelines

The Protocol Chair

The Protocol Chair, [name] is responsible for performing the following tasks:

- Coordinating, developing, submitting, and obtaining approval for the protocol as well as its subsequent amendments.
- Assuring that all participating institutions are using the correct version of the protocol.
- Taking responsibility for the overall conduct of the study at all participating institutions and for monitoring the progress of the study.
- Reviewing and ensuring reporting of Serious Adverse Events (SAEs).
- Reviewing data from all sites.

Lead Center

The Lead Center (Johns Hopkins University) is responsible for performing the following tasks:

- Ensuring that IRB approval has been obtained at each participating site prior to the first patient registration at that site, and maintaining copies of IRB approvals from each site.
- Managing central patient registration.
- Collecting and compiling data from each site.
- Establishing procedures for documentation, reporting and submitting of AE's and SAE's to the Protocol Chair and all other applicable parties.
- Facilitating audits by securing selected source documents and research records from participating sites for audit, or by auditing at participating sites.

Participating PCCTC Sites

Participating sites are responsible for performing the following tasks:

- Following the protocol as written, and the guidelines of Good Clinical Practice (GCP).
- Submitting data to the Lead Center.
- Registering all patients with the Lead Center by submitting patient registration form, and signed informed consent promptly.
- Providing sufficient experienced clinical and administrative staff and adequate facilities and equipment to conduct a collaborative trial according to the protocol.
- Maintaining regulatory binders on site and providing copies of all required documents to the Lead Center.
- Collecting and submitting data according to the schedule specified by the protocol.

10.1 Data Entry

Data collected during this study will be entered into a secure database. Staff at Johns Hopkins University will be responsible for the initial study configuration and setup in the CRMS database and for any future changes.

10.1.1 Case report forms completion

Electronic Case report forms will be generated by the coordinating center for the collection of all study data. Investigators will be responsible for ensuring that the CRFs are kept up-to-date.

The paper Eligibility Checklist CRF must be completed using black ink. Any errors must be crossed out so that the original entry is still visible, the correction clearly indicated and then initialed and dated by the individual making the correction.

eCRFs will be completed within 2 weeks of the patient coming to the clinic and all relevant supporting documentation such as scans, progress notes, nursing notes, blood work, pathology reports, etc., will be submitted via email to the SKCCC Coordinating Center Study Manager. All patient names or other identifying information will be removed prior to being sent to the Coordinating Center (SKCCC) or non-redacted source documents can be sent via a password-protected/secured document transfer based on each institution's guidelines.

Authorized representatives of the Coordinating Center (SKCCC) may visit the satellite sites to perform audits or inspections, including source data verification. The purpose of these audits or inspections is to systematically and independently examine all trial-related activities and documents to determine whether these activities were conducted and data were recorded, analyzed, and accurately reported according to the protocol, Good Clinical Practice (GCP), and any applicable regulatory requirements.

10.1.2 Source documents

Study personnel will record clinical data in each patient's source documents (i.e. the patient's medical record). Source documentation will be made available to support the patient research record. Study monitors will review entries on the CRFs at regular intervals, comparing the content with source documents.

10.1.3 Record retention

The investigator will maintain adequate and accurate records to enable the conduct of the study to be fully documented and the study data to be subsequently verified. After study closure, the investigator will maintain all source documents, study-related documents, and the CRFs. Because the length of time required for retaining records depends upon a number of regulatory and legal factors, documents should be stored until the investigator is notified that the documents may be destroyed. In this study, records are to be retained and securely stored for a minimum of 5 years after the completion of all study activities.

10.2 Data Management

10.2.1 Lead research program coordinators

A Lead research program coordinator at the coordinating center will be assigned to the study. A Lead Research Program Coordinator will manage the study activities at each of the participating sites. The responsibilities of the Lead Research Program Coordinator include project compliance, data collection, data entry, data reporting, regulatory monitoring, problem resolution and prioritization, and coordination of the activities of the protocol team.

10.3 Study Monitoring and Quality Assurance

Regularly scheduled registration reports will be generated to monitor patient accruals and the completeness of registration data. Routine data quality reports will be generated to assess missing data and inconsistencies. Accrual rates and the extent and accuracy of evaluations and follow-up will be monitored periodically throughout the study period, and potential problems will be brought to the attention of the principal investigator for discussion and action.

Random-sample data quality and protocol compliance audits will be conducted by the study team at least once a year, more frequently if indicated. Audits by the coordinating center may entail (1) shipping source documents and research records for selected patients from participating sites to the coordinating center for audit, or (2) on-site auditing of selected patient records at participating sites.

All clinical work conducted under this protocol is subject to Good Clinical Practice (GCP) guidelines. This includes inspection of study-related records by the lead site, sponsor, its designee, or health authority representatives at any time.

Data and Safety Monitoring:

The SKCCC Compliance Monitoring Program will provide external monitoring for JHU affiliated sites in accordance with SKCCC DSMP (Version 6.0, 02/21/2019). The SMC Subcommittee will determine the level of patient safety risk and level/frequency of monitoring. Additionally, scheduled meetings will take place monthly and will include the protocol principal investigator, research nurse, data manager, and, when appropriate, the collaborators, subinvestigators, and biostatistician involved with the conduct of the protocol.

Lead site/sponsor will conduct a quarterly reconciliation of SAEs with the BMS safety database by submitting an email request to [contact] and requesting the SAE reconciliation report followed by communication of any findings.

During these meetings the investigators will discuss matters related to: safety of protocol participants, validity and integrity of the data, enrollment rate relative to expectation, characteristics of participants, retention of participants, adherence to protocol (potential or real protocol violations), data completeness, and progress of data for secondary objectives.

10.4 Clinical Trial Agreement

This trial is being conducted under one or more clinical trial agreements that contain, among other terms, the publication policy, indemnity agreements, and financial arrangements for the study.

11. STATISTICAL CONSIDERATIONS

The sample size of 15 patients will provide a preliminary evaluation of clinical activity based on PSA response. Two-sided 95% Wilson confidence interval for various scenarios of PSA₅₀ response rate is presented in the table below:

Number of PSA ₅₀ response	Observed PSA ₅₀ response rate	95% confidence interval
3	20%	7.0 – 45.2%
4	26.7%	10.9 – 52.0%
5	33.3%	15.2 – 58.3%
6	40%	19.8 – 64.3%
7	46.7%	24.8 – 69.9%
8	53.3%	30.1 – 75.2%
9	60%	35.7 – 80.2%
10	66.7%	41.7 – 84.8%
11	73.3%	48.0 – 89.1%
12	80%	54.8 – 93.0%

11.1 Study Endpoints

11.1.1 Analysis of the primary endpoint

The primary endpoint of this study is PSA₅₀ response, defined as a decrease in the PSA to $\geq 50\%$ less than the baseline PSA upon enrollment in the trial. The decrease must be confirmed by a second measurement at least 4 weeks apart. For purposes of meeting the primary endpoint, patients will be considered to have done so if they have a PSA₅₀ response while on nivolumab. PSA values will be measured monthly during the trial. All patients who take at least one dose of nivolumab will be considered evaluable for the primary endpoint. If patients do not have at least one follow-up PSA after initiation of nivolumab due to stopping therapy for toxicity or withdrawing consent, then they will be replaced. PSA₅₀ response rate will be estimated along with 95% confidence interval.

We will estimate the PSA₅₀ response rate, along with the exact 95% confidence interval, for the population of patients.

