11.2 Analysis Populations

11.2.1 Intent-to-treat/Response-to-treatment/Evaluable population

All patients who meet eligibility criteria and receive at least 1 dose of nivolumab will be included in the main analysis of the response rate, even if there are major protocol deviations (e.g. incorrect treatment schedule or drug administration).

Conclusions are to be based on the population of all eligible patients. Subanalyses may be performed on various subsets of patients, such as those with no major protocol deviations or those who continued in the study for the entire treatment period (i.e. did not withdraw prematurely). Subanalysis will not serve as the basis for drawing conclusions concerning treatment efficacy.

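### Section 11.1.1 replaces some dosed patients who have no follow-up PSA without saying whether they stay in the primary denominator; dropping them could only raise the PSA50 rate

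*Combined protocol and SAP*

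**What the plan says.** - **Section 11.1.1, repeated in the synopsis (Statistical method, Primary Analysis):** "All patients who take at least one dose of nivolumab will be considered evaluable for the primary endpoint". The next sentence concerns dosed patients who lack even one PSA after starting nivolumab. Where this is "due to stopping therapy for toxicity or withdrawing consent, then they will be replaced". Nothing further is said about how such a patient is counted.
- **Section 11.2.1:** patients who are eligible and "receive at least 1 dose of nivolumab will be included in the main analysis of the response rate". Conclusions rest on all eligible patients. Analyses of subsets, such as those who did not withdraw early, may not support efficacy conclusions.
- **Size:** section 3.2 sets enrolment at 15. Section 11 says "The sample size of 15 patients will provide a preliminary evaluation of clinical activity based on PSA response", and its table is built on n = 15 only.
- **Response (11.1.1):** a PSA decline of at least 50% from baseline while on nivolumab. "The decrease must be confirmed by a second measurement at least 4 weeks apart".
- **PSA schedule:** Table 1 and sections 5.2.1 and 5.3 put a PSA at day 1 of each cycle and at the end-of-treatment visit, 28 days after the last dose.

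**The concern.** The trial has one arm, and its primary result is one proportion, so the denominator matters as much as the numerator. The replacement rule applies to men who have already been treated, and one of its two triggers, toxicity, can be a consequence of treatment. If a replaced man leaves the denominator, the plan removes patients who cannot be responders and puts in patients who stayed long enough to be measured.

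The plan also lacks the counting rule needed to compute the rate. No section says that a dosed patient with no post-baseline PSA is a non-responder. Two analysts could each follow the text faithfully and report different primary results from the same data. That should be settled before the data are seen.

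**Working it through.** **1. The plan's own figures.** Section 11 gives a "Two-sided 95% Wilson confidence interval for various scenarios" of the response rate at n = 15. The Wilson limits are [p + z²/2n ± z√(p(1−p)/n + z²/4n²)] / (1 + z²/n). With p = 6/15 = 0.40 and z = 1.96:

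- centre = (0.40 + 0.128)/1.256 = 0.420
- half-width = 1.96 × √(0.0160 + 0.0043)/1.256 = 0.222
- limits = 19.8% to 64.3%, as tabulated

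All ten rows of the table reproduce to one decimal. Section 11.1.1 instead plans the rate "along with the exact 95% confidence interval, for the population of patients", which for 6/15 is 16.3% to 67.7%. Both types of interval are therefore shown in step 4.

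**2. Can a replaced patient be a responder?** A confirmed response needs a qualifying post-baseline PSA and a second one at least 4 weeks apart. A man with no follow-up PSA has neither. He adds 0 to the numerator whichever way he is counted, so only the denominator is in question.

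**3. Effect of dropping him.** Let x be the responders among 15 retained patients and k the number replaced.

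- Rate if dropped: x/15
- Rate if kept: x/(15 + k)
- Ratio: (15 + k)/15 = 1.07, 1.13 and 1.20 for k = 1, 2, 3
- Difference: xk/[15(15 + k)], which is positive whenever x and k are at least 1

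The documents give no value for k; 1 to 3 is an assumed range.

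| Responders x | Dropped (n = 15) | Kept, k = 1 | Kept, k = 2 | Kept, k = 3 |
|---|---|---|---|---|
| 3 | 20.0% | 18.8% | 17.6% | 16.7% |
| 6 | 40.0% | 37.5% | 35.3% | 33.3% |
| 9 | 60.0% | 56.3% | 52.9% | 50.0% |
| 12 | 80.0% | 75.0% | 70.6% | 66.7% |

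Example: x = 6, k = 1 gives 6 × 1/(15 × 16) = 0.025, or 2.5 points. The smallest difference in the table is 3/240 = 1.25 points and the largest is 36/270 = 13.3 points.

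**4. Intervals for x = 6.**

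| n | Rate | Wilson 95% | Exact 95% |
|---|---|---|---|
| 15 | 40.0% | 19.8–64.3 | 16.3–67.7 |
| 16 | 37.5% | 18.5–61.4 | 15.2–64.6 |
| 17 | 35.3% | 17.3–58.7 | 14.2–61.7 |
| 18 | 33.3% | 16.3–56.3 | 13.3–59.0 |

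**5. Who is affected?** A man who stops for toxicity after one dose is still due a PSA 28 days later at the end-of-treatment visit. If he attends, he has a follow-up PSA and the rule does not reach him. It reaches only men who also miss that PSA, or who withdraw consent before it.

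**The case against.** The strongest reply is that replacement can simply mean recruiting additional patients while every eligible dosed patient stays in the analysis. The text nowhere calls a replaced patient excluded or not evaluable. The sentence just before the rule says that all dosed patients are evaluable. Section 11.2.1 says the same of eligible dosed patients, and it bars conclusions from analyses that leave out early withdrawals. On that reading there is neither bias nor contradiction.

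This stands to a point. A reader might infer that the plan definitely removes non-responders and so has a biased primary analysis. The documents do not support that as a settled fact, because removal is an inference from one word. A reader might also infer that anyone who stops for toxicity in the first cycle is swapped out. The end-of-treatment PSA shows otherwise. Nor is consent withdrawal, the other trigger, tied to treatment in the text.

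The benign reading still leaves gaps. Nothing provides for n above 15 in section 3.2 or in the precision table. If every dosed patient stays in, the section does not say what replacement is for. And no rule says how a man without a follow-up PSA is counted.

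It is also fair to say that the shift is small beside the uncertainty: 2.5 points for one replacement at 6 responders, against an exact interval about 51 points wide (67.7 − 16.3).

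**Conclusion.** The point holds as an unresolved rule whose ordinary reading would bias the only primary estimate upward. It does not hold as proof that the plan drops these patients.

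If they are dropped, the all-treated rate is overstated by a factor of (15 + k)/15. At 6 responders, 40.0% stands in place of 37.5%, 35.3% or 33.3% for one, two or three replacements. If they are kept, as section 11.2.1 requires, there is no bias and n is 15 + k. These figures assume k between 1 and 3 and at least one responder. The true k is not given and may well be 0 or 1, given the scheduled end-of-treatment PSA.

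A reader might infer an inflated type I error or a distorted go/no-go decision. There is none to distort: the plan sets no null rate, test or decision threshold. What is affected is the reported proportion and its interval. It still merits correction, because the rule is written into the primary-endpoint section, works in one direction only, and is easily settled in advance.

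**What to change.** In section 11.1.1 and the synopsis, state that:

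- the primary denominator is the section 11.2.1 population, that is, all eligible patients with at least one dose (11.1.1 currently omits eligibility, so a cross-reference also removes that mismatch);
- patients in it with no post-baseline PSA, for whatever reason, count as non-responders;
- any replacement is extra accrual, and the original patient stays in the denominator.

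In section 3.2 and the opening of section 11, note that the number analysed may then exceed 15. Report the rate among patients with at least one follow-up PSA only as a sensitivity analysis, in line with the limit that 11.2.1 already places on subset analyses.

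The cost is a few sentences in four places. No patients are needed beyond those the replacement rule already implies. The downside is that the reported rate may be slightly lower.

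### The sample size of 15 is supported by Wilson intervals, but the primary analysis is to report the exact interval, which is wider on every tabulated row

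*Combined protocol and SAP*

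**What the plan says.** Section 11 (Statistical Considerations) opens with the basis for the sample size: "The sample size of 15 patients will provide a preliminary evaluation of clinical activity based on PSA response". It then introduces a table headed "Two-sided 95% Wilson confidence interval for various scenarios of" the PSA50 response rate, with rows for 3 to 12 responders out of 15. The synopsis repeats the sentence and the table under its sample size heading. The plan gives no null rate, power or target width, so the table is all the quantitative support that n = 15 has.

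Section 11.1.1 describes the primary analysis. One sentence promises a 95% confidence interval and names no method. The next says that the rate will be estimated "along with the exact 95% confidence interval, for the population of patients". The primary analysis paragraph of the synopsis has only the unspecific sentence. Nowhere is Wilson named as the analysis method, and nowhere is the difference between table and analysis explained.

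**The concern.** Wilson is a score-based approximation. An exact interval inverts binomial tail probabilities, or an exact test, and at n = 15 the two differ visibly. A reader who takes the table as the precision that the trial will report will expect narrower intervals than section 11.1.1 will produce.

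This matters because the interval around the PSA50 rate is the main result of a small uncontrolled trial. Near a rate that readers have in mind, the method can decide which side of it a limit falls on. Section 1.3.1 offers one such rate: about 40% for PD-1/PD-L1 inhibitors in dMMR/MSI-H metastatic castrate-resistant disease.

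**Working it through.** **Inputs.** n = 15, two-sided 95% (z = 1.96), and responses x = 3 to 12, all from section 11. The analysis method, exact, is from section 11.1.1. The denominator is taken as 15, as in the plan's table. Section 11.1.1 says "All patients who take at least one dose of nivolumab will be considered evaluable for the primary endpoint" and replaces patients who stop for toxicity or withdraw consent without a follow-up PSA.

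**Step 1: reproduce the plan's table.** With p = x/n, the Wilson limits are

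[p + z²/(2n) ± z·√(p(1−p)/n + z²/(4n²))] / (1 + z²/n).

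For x = 10: p = 0.6667, z²/(2n) = 0.1280, the square-root term times z is 0.2708, and the divisor is 1.2561. The limits are (0.7947 − 0.2708)/1.2561 = 0.417 and (0.7947 + 0.2708)/1.2561 = 0.848. The plan gives 41.7 – 84.8%. All 20 tabulated limits reproduce to one decimal.

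**Step 2: the exact interval, read as Clopper-Pearson.** The lower limit is the 0.025 quantile of Beta(x, n−x+1). The upper limit is the 0.975 quantile of Beta(x+1, n−x). Extra width is computed from unrounded limits.

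| Responses | Plan's table (Wilson), % | Clopper-Pearson, % | Extra width, points |
|---|---|---|---|
| 3 | 7.0–45.2 | 4.3–48.1 | 5.62 |
| 4 | 10.9–52.0 | 7.8–55.1 | 6.26 |
| 5 | 15.2–58.3 | 11.8–61.6 | 6.69 |
| 6 | 19.8–64.3 | 16.3–67.7 | 6.95 |
| 7 | 24.8–69.9 | 21.3–73.4 | 7.07 |
| 8 | 30.1–75.2 | 26.6–78.7 | 7.07 |
| 9 | 35.7–80.2 | 32.3–83.7 | 6.95 |
| 10 | 41.7–84.8 | 38.4–88.2 | 6.69 |
| 11 | 48.0–89.1 | 44.9–92.2 | 6.26 |
| 12 | 54.8–93.0 | 51.9–95.7 | 5.62 |

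Total widths are 43.8 to 52.1 points against 38.1 to 45.1 for Wilson, a relative increase of about 15 to 16%. Each limit moves outward by about 2.7 to 3.5 points.

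**Step 3: sensitivity to the meaning of exact.** Inverting the two-sided exact binomial test (the minimum-likelihood interval) gives an extra width of 2.7 to 3.3 points over the same rows. The direction is unchanged and the size is roughly halved.

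**Step 4: an example against the plan's own context.** At 10/15 the lower limits are 41.7% (Wilson), 38.4% (Clopper-Pearson) and 39.7% (minimum-likelihood). Only the Wilson interval lies wholly above 40%. The two-sided minimum-likelihood exact test of 40% at 10/15 gives p of about 0.06, which agrees.

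**The case against.** The strongest reply is that nothing in the design fails. The table is openly labelled Wilson, it illustrates scenarios, and the text promises only a preliminary look at activity. No target width, null rate or go/no-go rule was set, so 15 was not solved from the tabulated widths. This stands. A reader might infer that the trial is undersized, or that it misses an operating characteristic, but the documents commit to none.

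A second reply is that part of the extra width is Clopper-Pearson's conservatism. Averaged over true rates from 10% to 90% at n = 15, coverage is 95.4% for Wilson (minimum 91.4%) and 97.7% for Clopper-Pearson (minimum 95.2%). This also stands: the Wilson table is a fair picture of 95% precision as such. It is not a picture of the interval that section 11.1.1 says will be reported.

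Third, the 40% in section 1.3.1 is neither a null nor described as a PSA50 rate, and it comes from a different disease state. That is correct, so the 10/15 example is context only. Other rates are weaker still. A reader might note that Wilson excludes 5% at 3/15 where Clopper-Pearson does not. But the plan never uses 5%, and the minimum-likelihood interval (lower limit 5.7%) excludes it too.

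Finally, a reader might infer that section 11.1.1 leaves the analyst free to choose between two methods once the data are in. The text gives this little support. The unspecific sentence is followed at once by one naming the exact interval, and the natural reading is that the second specifies the first.

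**Conclusion.** The point holds as an inconsistency between the sample-size justification and the planned analysis. It is not a calculation error: a reader who infers that the table is wrong would be mistaken, since every row is correct for the method on its label.

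Assuming that exact means Clopper-Pearson, the usual reading though not stated, and that 15 patients are analysed, the tabulated intervals are too narrow by 5.6 to 7.1 points of total width. Under a minimum-likelihood exact interval the shortfall is 2.7 to 3.3 points. The sample size, the form of the analysis and any decision from the trial are unaffected. What changes is the precision that readers are led to expect. The correction is worth making because it concerns the sole primary estimate and costs very little.

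**What to change.** Name one interval method, in the same words, in four places: the synopsis primary analysis, the synopsis sample size paragraph, section 11 and section 11.1.1. Either option resolves the point.

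- **Wilson throughout.** Change exact to Wilson in section 11.1.1 and leave both copies of the table as they are. This costs one word there, plus naming the method in the synopsis. The trade-off is that Wilson does not guarantee at least 95% coverage at every true rate.
- **Exact throughout.** Keep exact, specify Clopper-Pearson, and replace the intervals in both copies of the table with the Clopper-Pearson column above, changing the Wilson label to match. This costs one table, and the stated precision becomes slightly less favourable.

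In section 11.1.1, merge the two sentences on the confidence interval into one that names the method.
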